8.4.5 Pregnancy and Exposure During Breastfeeding

Although pregnancy and infant exposure during breastfeeding are not considered AEs, any pregnancy or infant exposure during breastfeeding in a participant (spontaneously reported to the investigator or their designee) that occurs during the study are reportable to the Sponsor.

All reported pregnancies must be followed to the completion/termination of the pregnancy.

Any pregnancy complication will be reported as an AE or SAE.

The medical reason (example: maternal health or fetal disease) for an elective termination of a pregnancy will be reported as an AE or SAE. Prenatal testing showing fetus will be born with severe abnormalities/congenital anomalies that leads to an elective termination of a pregnancy will be reported as an SAE for the fetus.

Pregnancy outcomes of ectopic pregnancy, spontaneous abortion, missed abortion, benign hydatidiform mole, blighted ovum, fetal death, intrauterine death, miscarriage, and stillbirth must be reported as serious events (Important Medical Events). If the pregnancy continues to term, the outcome (health of infant) must also be reported.

8.4.6 Disease-related Events and/or Disease-related Outcomes Not Qualifying as AEs or SAEs

This is not applicable to this study.

8.4.7 Events of Clinical Interest

There are no ECIs for this study.

8.4.8 Medical Device and Drug–Device Combination Products – PQCs/Malfunctions

The method of documenting and reporting of such events (complaints associated with medical devices including PQCs/malfunctions) will occur as below and in Appendix 4.

To fulfill regulatory reporting obligations worldwide, medical device information associated with AEs will be collected and reported to the Sponsor in the same time frame as AEs per Section 8.4.1 via CRF (paper or electronic) and as per data entry guidelines.

PQCs/malfunctions including those that involve a participant or any user/associated person must be reported to the Sponsor. Sponsor shall review reported events by the investigator to fulfill the legal responsibility of notifying appropriate regulatory authorities and other entities about certain safety information relating to medical devices and drug-device combination products being used in clinical studies.

The investigator is responsible for ensuring that follow-up includes any supplemental investigations as indicated to elucidate the nature and/or causality between the AE and the medical device or device constituent of combination product.

8.4.9 Adverse Events on the VRC

Participants will use an eVRC to report solicited and unsolicited AEs.

The definitions of solicited and unsolicited AEs can be found in Appendix 3.

8.4.9.1 Solicited Adverse Event

Solicited AEs for this study are summarized in [Table 6](#).

Table 6 **Solicited Adverse Events**

Type of Solicited Adverse Event	Predefined Solicited Adverse Events (Preferred Term)	Solicited Time Period
Injection Site	Left arm (postvaccination with 9vHPV vaccine) 
• Injection-site pain/tenderness• Injection-site swelling• Injection-site redness (erythema) Right arm (postvaccination with mRNA-1273 vaccine) 
• Injection-site pain/tenderness• Injection-site swelling• Injection-site redness (erythema)• Underarm gland swelling or tenderness (lymphadenopathy)	Day 1 to Day 7 postvaccination
Systemic	
• Headache• Fatigue• Muscle aches all over the body (myalgia)• Joint aches in several joints (arthralgia)• Nausea• Vomiting• Chills	Day 1 to Day 7 postvaccination

All solicited injection-site AEs will be considered related to study intervention.

In addition, the investigator will review all solicited AEs for the following:

- Is the event a symptom of another diagnosis?
- Is the event ongoing at the end of the solicited period?
- Does the event meet serious criteria?

A solicited AE that meets any of the above criteria must also be reported on the appropriate eCRF as specified in the data entry guidelines.

8.4.9.2 Unsolicited Adverse Events

Unsolicited AEs for this study are events that are 1) not predefined in [Table 6](#), or 2) predefined in [Table 6](#) but reported at any time outside the solicited time period.

As detailed in Section 8.4, the investigator will assess unsolicited AEs that meet the definition of an AE or SAE with respect to seriousness, intensity, and causality.

8.5 Treatment of Overdose

In this study, an overdose is defined as a participant receiving >1 dose of any individual study vaccine in a 24-hour period or >2 doses of any individual study vaccine throughout the study.

Sponsor does not recommend specific treatment for an overdose.

Decisions regarding dose interruptions or modifications will be made by the investigator in consultation with the Sponsor Clinical Director based on the clinical evaluation of the participant.

All reports of overdose must be reported by the investigator within 5 calendar days to the Sponsor either by electronic media or paper. Electronic reporting procedures can be found in the EDC data entry guidelines. Paper reporting procedures can be found in the Investigator Study File Binder (or equivalent).

8.6 Pharmacokinetics

PK parameters will not be evaluated in this study.

8.7 Pharmacodynamics

Pharmacodynamic parameters will not be evaluated in this study.

8.8 Biomarkers

Biomarkers are not evaluated in this study.

8.9 Future Biomedical Research Sample Collection

If the participant provides documented informed consent/assent for FBR, the following specimens will be obtained as part of FBR:

- DNA for future research
- Leftover main study serum from anti-HPV antibody testing stored for future research
- Leftover main study serum from SARS-CoV-2 spike protein-specific binding antibody testing stored for future research

8.10 Medical Resource Utilization and Health Economics

Medical Resource Utilization and Health Economics are not evaluated in this study.

8.11 Visit Requirements

Visit requirements are outlined in Section 1.3. Specific procedure-related details are provided in Section 8.

8.11.1 Screening

The Screening Visit or the last Screening Visit (for rescreening) should be on the same day of enrollment and the first dose of vaccination. Potential participants will be evaluated to determine that they fulfill the entry requirements as provided in Section 5. Screening procedures may be repeated after consultation with the Sponsor.

8.11.2 Intervention and Follow-up Periods

Requirements during the intervention and follow-up periods are outlined in Section 1.3.

8.11.3 Participants Discontinued From Study Intervention but Continuing to be Monitored in the Study

Participants who discontinue study vaccination but continue in the study will attend study visits as provided in Section 1.3; however, serum will not be collected.

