4 STUDY DESIGN

4.1 Overall Design

This is a randomized, open-label, multicenter study to evaluate the safety and immunogenicity of a 2-dose regimen of 9vHPV vaccine, where the first dose is administered concomitantly with a first dose of a 2-dose regimen of mRNA-1273 vaccine versus nonconcomitant administration of 9vHPV and mRNA-1273 vaccines in boys and girls 9 to 11 years of age. Approximately 160 participants will be randomly assigned in a 1:1 ratio to 1 of the following groups:

Concomitant Group: Participants will receive their first dose of 9vHPV vaccine and first dose of mRNA-1273 vaccine on Day 1; they will then receive their second dose of mRNA-1273 vaccine at Month 1 and their second dose of 9vHPV vaccine at Month 6.

Nonconcomitant Group: Participants will receive their first and second doses of mRNA-1273 vaccine on Day 1 and at Month 1, respectively; they will then receive their first and second doses of 9vHPV vaccine at Months 2 and 8, respectively.

Blood samples for immunogenicity assays will be collected prior to the first dose of each vaccine and 4 weeks Postdose 2 of each vaccine.

After completion of immunogenicity testing to evaluate the study objectives, all leftover serum samples will be stored to conduct any additional study-related testing as required by regulatory agencies or the Sponsor. For study participants who provided consent for future biomedical research, leftover sera from the study will be deidentified and may be used for other purposes such as the development and/or validation of HPV assays or biomarker development after completion of all study-related immunogenicity testing (Section 8.9).

Participants will be followed for local and systemic AEs from Day 1 through Day 28 following each vaccination (see Section 8.4.1). Information for all AEs resulting in discontinuation from study, MAAEs (see Section 10.3.1), and SAEs, regardless of whether the events are considered to be vaccine-related by the investigator, will be collected from the time consent is signed through completion of participation in the study (see Section 8.4.1).

Specific procedures to be performed during the study, including prescribed times and associated visit windows, are outlined in Section 1.3 of the SoA. Details of each procedure are provided in Section 8.

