6.4 Study Intervention Compliance

Interruptions from the protocol-specified vaccination plan specified in Section 1.3 require consultation between the investigator and the Sponsor and written documentation of the collaborative decision on participant management.

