7 DISCONTINUATION OF STUDY INTERVENTION AND PARTICIPANT WITHDRAWAL

7.1 Discontinuation of Study Intervention

Discontinuation of study intervention does not represent withdrawal from the study.

As certain data on clinical events beyond study intervention discontinuation may be important to the study, they must be collected through the participant's last scheduled follow-up, even if the participant has discontinued study intervention. Therefore, all participants who discontinue study intervention before completion of the protocol-specified vaccination regimen will still continue to participate in the study as specified in Section 1.3 and Section 8.11.3.

Participants may discontinue study intervention at any time for any reason or be discontinued from the study intervention at the discretion of the investigator should any untoward effect occur. In addition, a participant may be discontinued from study intervention by the investigator or the Sponsor if study intervention is inappropriate, the study plan is violated, or for administrative and/or other safety reasons. Specific details regarding procedures to be performed at study intervention discontinuation are provided in Section 8.1.10 and Section 8.11.3.

A participant must be discontinued from study intervention, but continue to be monitored in the study, for any of the following reasons:

- The participant or participant's legally acceptable representative requests to discontinue study intervention.
- **For mRNA-1273 vaccine only:** The participant experiences 1 or more of the following AEs assessed as clearly related to the mRNA-1273 vaccine after receiving the first dose: multisystem inflammatory syndrome in children, myocarditis, pericarditis, anaphylaxis, or generalized urticaria. In this case, the second dose of the mRNA-1273 vaccine must be discontinued.
 - **Note:** In addition to the stopping rule above, in the event that ≥ 2 participants experience myocarditis and/or pericarditis per the CDC case definition (Section 10.3.1), then all further doses of mRNA-1273 vaccine for participants enrolled in the study must be discontinued (Section 4.4.1).
- The participant has a medical condition or personal circumstance which, in the opinion of the investigator and/or Sponsor, places the participant at unnecessary risk from continued administration of study intervention.

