For participants who are discontinued from study intervention, but continue to be monitored in the study, see Section 1.3 and Section 8.11.3 for those procedures to be completed at each specified visit.

Discontinuation from mRNA-1273 vaccine or 9vHPV vaccine is “permanent.” Once a participant is discontinued from a study intervention, they shall not be allowed to restart the same study intervention; however, the participant may be administered the other study intervention as scheduled.

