8.1.10 Discontinuation and Withdrawal

Participants who discontinue study intervention before completion of the vaccination regimen should be encouraged to continue to be followed for all remaining study visits as outlined in the SoA and Section 8.11.3.

Participants who discontinue either study vaccine may receive the other study vaccine.

Participants who withdraw from the study should be encouraged to complete all applicable activities scheduled for the review of safety data at the time of withdrawal. Any AEs that are present at the time of withdrawal should be followed in accordance with the safety requirements outlined in Section 8.4.

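### Section 8.11.3 stops all serum once study vaccination is discontinued, without separating one vaccine from both, so a child who completes one vaccine can lose that vaccine's primary-endpoint sample

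*Combined protocol and SAP*

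**What the plan says.** Section 8.11.3 covers participants who discontinue study vaccination but remain in the study. They "will attend study visits as provided in Section 1.3; however, serum will not be collected".

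Section 7.1 lists the reasons for discontinuing study intervention while staying under observation. One is a request: the participant or the "legally acceptable representative requests to discontinue study intervention". Another applies to mRNA-1273 alone, after certain adverse events following dose 1: "In this case, the second dose of the mRNA-1273 vaccine must be discontinued". For discontinued participants the section says to "see Section 1.3 and Section 8.11.3 for those procedures to be completed at each specified visit". It then makes discontinuation vaccine-specific: "they shall not be allowed to restart the same study intervention; however, the participant may be administered the other study intervention as scheduled". Section 8.1.10 repeats this: "Participants who discontinue either study vaccine may receive the other study vaccine".

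Section 4.1 plans sampling around each vaccine: "Blood samples for immunogenicity assays will be collected prior to the first dose of each vaccine and 4 weeks Postdose 2 of each vaccine".

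In the schedule of activities (Section 1.3), the spike-antibody samples are at Day 1 and Visit 3 (Month 2) in both groups. The anti-HPV samples are at Day 1 and Month 7 in the Concomitant Group, and at Month 2 and Month 9 in the Nonconcomitant Group.

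**The concern.** Section 7.1 routes a child who has stopped only one vaccine to a section that ends serum collection without qualification. That child may go on to complete the other vaccine and so supply a valid primary immunogenicity outcome for it, yet the text tells the site not to draw the sample.

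A sample not taken in its window cannot be replaced. Table 9 specifies observed data only, so the child drops out of the analysis of that vaccine. Sites that read the sentence differently would also collect different data from similar children.

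**Working it through.** **1. Which samples are lost on the literal reading**

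| Discontinuation | Vaccine completed | Concomitant Group loses | Nonconcomitant Group loses |
|---|---|---|---|
| mRNA-1273 after dose 1 | 9vHPV | Month 7 anti-HPV | Month 2 pre-9vHPV and Month 9 anti-HPV |
| 9vHPV stopped or declined before the Visit 3 draw | mRNA-1273 | Month 2 spike | Month 2 spike |
| 9vHPV after Visit 3 | mRNA-1273 | no spike sample | no spike sample |

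The Month 2 pre-9vHPV sample matters in its own right, because criterion 2 of the HPV per-protocol population (Section 9.5.1) requires baseline seronegativity.

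**2. Other sections that point the other way**

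- Section 4.1 ties sampling to each vaccine's own doses. It is a general sentence and does not address discontinuation.
- Section 8.3.6 ends mRNA-1273 dosing if pregnancy is found before its second dose, yet Table 4 calls for blood 4 weeks after a later second 9vHPV dose. On schedule this can arise only in the Concomitant Group, because Nonconcomitant children do not start 9vHPV until Month 2.
- Section 4.4.1 allows 9vHPV dosing and laboratory procedures to continue after a study-wide mRNA-1273 stop. Its wording is permissive, so this is a tension and not a contradiction.

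**3. Does the loss reach the planned analyses?**

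Criterion 1 of each per-protocol population in Section 9.5.1 requires all planned vaccinations with the correct dose of the named vaccine. If it concerns that vaccine only, these children would qualify but for the missing serum. If it means both vaccines, they are excluded anyway and the lost serum changes no planned analysis. Having two separate populations, each naming its own vaccine, favours the first reading.

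**4. Effect on precision**

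Inputs from Table 11: 80 enrolled per group; HPV 45 with CV 1.38 and 9% exclusion; SARS-CoV-2 with log SD 1.5 and 10% exclusion.

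Half-width = t(0.975, n1 + n2 − 2) × SD × √(1/n1 + 1/n2), with SD = √ln(1 + CV²) for HPV.

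The plan's own figures come first:

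- HPV 45: SD = √ln(1 + 1.38²) = 1.0326; n = 80 × 0.91 = 72.8; 1.9766 × 1.0326 × √(2/72.8) = 0.3383 (Table 11: 0.338).
- SARS-CoV-2: n = 80 × 0.90 = 72; 1.9768 × 1.5 × √(2/72) = 0.4942 (Table 11: 0.494).

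The documents give no rate of single-vaccine discontinuation, so the numbers lost are assumptions:

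| Lost | HPV 45, each group | SARS-CoV-2, one group | SARS-CoV-2, each group |
|---|---|---|---|
| 0 | 0.338 | 0.494 | 0.494 |
| 1 | 0.341 | 0.496 | 0.498 |
| 2 | 0.343 | 0.498 | 0.501 |
| 4 | 0.348 | 0.502 | 0.509 |

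At a true ratio of 1.0 the interval is exp(±half-width). With two lost per group it moves from 0.713–1.403 to 0.710–1.409 for HPV 45, and from 0.610–1.639 to 0.606–1.651 for SARS-CoV-2.

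**The case against.** The best counter-argument is that 8.11.3 can be read as covering only children who stop both vaccines. A child still receiving 9vHPV has arguably not discontinued study vaccination, and the protocol uses narrower wording in 7.1 and 8.1.10 when it means a single product. Section 4.4.1 and Table 4 fit that reading. It remains possible, but it is stated nowhere. It also sits poorly with Section 7.1, which lists an mRNA-1273-only stop among the discontinuations it sends to 8.11.3.

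Second, the harm requires a broad reading of 8.11.3 together with a vaccine-specific reading of criterion 1 in 9.5.1. That is correct, and it limits the finding.

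Third, the cases are rare. No mandatory stop in 7.1 is specific to 9vHPV, so losing the spike sample requires a family to stop 9vHPV before Month 2 or, in the Nonconcomitant Group, to decline it before it has started. The Table 4 case is rarer still. This also stands.

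Fourth, Section 6.4 says that interruptions of the vaccination plan "require consultation between the investigator and the Sponsor and written documentation of the collaborative decision on participant management". That gives the sponsor an occasion to settle the matter child by child. It is a partial safeguard, because it does not mention serum and supplies no sampling rule.

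**Conclusion.** The concern holds as a minor inconsistency. On its plain wording, 8.11.3 withholds primary-endpoint serum for a vaccine the child has completed, in two situations: an mRNA-1273-only stop, and a 9vHPV stop before the Visit 3 draw. This is inconsistent with the vaccine-by-vaccine sampling in 4.1 and, in a rare case, with Table 4; it is in tension with 4.4.1.

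The size is very small. With an assumed one to four children lost per group, the half-widths rise by at most 0.010 for HPV 45 (0.348 − 0.338) and 0.015 for SARS-CoV-2 (0.509 − 0.494). No hypothesis is tested. Bias is possible but not shown. The effect on the per-protocol sets depends on criterion 1 being vaccine-specific. The reason to act is that the loss is avoidable and irreversible.

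**What to change.** Amend Section 8.11.3 to say that the scheduled baseline and Postdose 2 sera are collected for any vaccine whose regimen the participant is continuing or has completed, and reconcile it with Sections 4.1, 4.4.1, 7.1, 8.1.10 and 8.3.6 (Table 4). Whether serum is still drawn for the discontinued vaccine is a separate choice for the sponsor. It does not affect the per-protocol analyses, because that child already fails criterion 1 for that vaccine. If criterion 1 is meant to cover each vaccine's own doses only, a sentence in 9.5.1 could say so at the same time.

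The cost is a short amendment, with the regulatory submission and ethics review described in Section 10.1.1, so it is best combined with another amendment. The running cost is a few assays. No new draws are needed: the samples are already scheduled, and 6 + 6 + 5 + 5 + 8.5 = 30.5 mL (Tables 2 and 3) equals the maximum set in Section 8. No dosing or stopping rule changes.

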9 STATISTICAL ANALYSIS PLAN

This section outlines the statistical analysis strategy and procedures for the study. If, after the study has begun, but prior to final database lock, changes are made to primary hypotheses, or the statistical methods related to those hypotheses, then the protocol will be amended (consistent with ICH Guideline E-9). Changes to exploratory or other nonconfirmatory analyses made after the protocol has been finalized, but prior to final database lock, will be documented in an sSAP and referenced in the CSR for the study. Posthoc exploratory analyses will be clearly identified in the CSR.

9.1 Statistical Analysis Plan Summary

Key elements of the statistical analysis plan are summarized below; the comprehensive plan is provided in Sections 9.2 to 9.12.

Study Design Overview	A Phase 3, Multicenter, Open-Label Study to Evaluate the Safety and Immunogenicity of 2-dose Regimens of 9vHPV and mRNA-1273 SARS-CoV-2 Vaccines Where the First Dose of Each Vaccine Are Given Concomitantly in Boys and Girls 9 to 11 Years of Age
Treatment Assignment	Study participants will be randomized in a 1:1 ratio between the Concomitant and Nonconcomitant Groups. No stratification will be implemented during randomization.
Analysis Populations	Immunogenicity: Per-protocol population Safety: APaT population
Primary Endpoint(s)	Immunogenicity: 1. cLIA anti-HPV 6, 11, 16, 18, 31, 33, 45, 52, and 58 titers. 2. SARS-CoV-2 spike protein-specific binding antibody concentration. Safety: 1. Solicited injection-site AEs Day 1 through Day 7 postvaccination. 2. Solicited systemic AEs Day 1 through Day 7 postvaccination. 3. SAEs Day 1 through Day 28 postvaccination. 4. Vaccine-related SAEs observed any time during the study.
Key Secondary Endpoints	Immunogenicity: 
Seroconversion to HPV Types 6, 11, 16, 18, 31, 33, 45, 52, and 58 based on cLIA.Seroresponse to SARS-CoV-2 based on SARS-CoV-2 ECL assay.
Statistical Methods for Key Immunogenicity Analyses	Evaluation of primary and secondary objectives will be performed separately for each immunogenicity parameter. Analysis of variance modeling will be used. The response variable is the natural logarithm of the relevant antibody titers and an indicator variable representing the concomitant vaccination group will be a fixed effect. Point estimates of the GMTs/GMC and corresponding within-group 95% CIs as well as geometric mean ratio and corresponding 95% CI of the geometric mean ratio will be derived from the estimate of the fixed effect.
Statistical Methods for Key Safety Analyses	By-treatment group summaries of safety endpoints will be provided in terms of treatment group-specific counts and proportions (or percent) of participants who are cases of particular safety endpoints. Confidence intervals of risk difference (difference in percent or proportions), when provided, will be calculated using the M&N method [Miettinen, O. and Nurminen, M. 1985].
Interim Analyses	No interim analyses are planned for this study.
Multiplicity	No multiplicity adjustment will be required, as there is no formal hypothesis testing.
Sample Size and Power	The expected total sample size is approximately 160 participants. Participants are to be randomly assigned in a 1:1 ratio to the Concomitant Group and Nonconcomitant Group. Immunogenicity: This is an estimation study. There are no hypotheses to be evaluated. Safety: Section 9.9.2 provides information about the ability of this study to estimate the incidence of AEs within the Concomitant and Nonconcomitant Groups.

